12 SUBGROUP ANALYSIS

	will be summarized by the following subgroups in Table 2.	
Table 2Subgroups Defined at Baseline		
Subgroup	Values	
Age group 1	≤ median age > median age	
Age group 2	\leq 40 years old > 40 years old	
Race	White Non-white (American Indian or Alaska Native, Asian, Black or African American, Native Hawaiian or Other Pacific Islander)	
Region	America Europe	
Ethnicity	Hispanic or Latino Not Hispanic or Latino	
Surgical group	Each of the surgical groups	
Baseline BCVA	≤ median baseline BCVA > median baseline BCVA	
Microperimetry mean sensitivity	<pre>≤ median baseline mean sensitivity</pre> > median baseline mean sensitivity	
Microperimetry fixation	Unstable/relatively unstable Stable	
Location of preserved autofluorescence on FAF	Non-subfoveal Subfoveal	
ADA	Positive Negative	
Nab	Positive Negative	
ELISpot (overall treatment of BIIB111)	Positive Negative	

The primary and key secondary efficacy endpoints along with the

13 DROP OUT PROFILE

The number, pattern and timing of missing data will be examined by treatment group along with the reasons for withdrawal or for missing data.

The pattern of missing data due to discontinuation will be characterised by summarising the time to discontinuation based on the Kaplan-Meier estimates and the corresponding Kaplan-Meier curves. Time to discontinuation is calculated as the date of discontinuation – date of Visit 2 (i.e., surgery or phone contact) + 1.

14 APPENDICES

Language	Text	Number of Words
English	1 – Mice	156
	2 – Beaver	161
	3 – Trees	156
	4 – Prey	165
	5 – Desert	155
	6 – Venom	136
	7 – Island	158
	8 – Spiders	159
	9 – Winter	148
	10 – Colors	141
German	1 – Mäuse	132
	2 – Biber	137
	3 – Bäume	131
	4 – Beute	138
	5 – Wuste	133
	6 – Gift	129
	7 – Inseln	130
	8 – Spinnen	130
	9 – Winter	133
	10 – Farbe	129
Dutch	1 – Muizen	141
	2 – Bever	147
	3 – Bomen	139
	4 – Buit	146
	5 – Woestijnen	138
	6 – Gif	141
	7 – Eilanden	146
	8 – Spinnen	140
	9 – Winter	138
	10 – Kleur	138
Finnish	1 – Hiiret	100
	2 – Majava	104
	3 – Puut	102
	4 – Saalis	104
	5 – Aavikko	105
	6 – Myrkky	102
	7 – Saaret	107
	8 – Hämähäkit	99
	9 – Talvi	94
	10 – Värit	98

14.1 Appendix 1: IRest Reading Speed Test, Conversion Table

Biogen / NightstarRx, Ltd	
BIIB111	

14.2 Appendix 2: Schedule of Study Procedures

Visit	Visit 1ª	Visit 2 ^b	Visit 3 ^b	Visit 4 ^b	Visit 5ª	Visit 6ª	Visit 7ª	Visit 8 ^{a, c}	Early Termination ^d	Unscheduled Visit ^e
Study Day/Visit Window	Screening/ Baseline ^f	Day 0 Injection Day	Day 1 Post op	Day 7 Post op ± 3d	Month 1 ± 7d	Month 4 ± 7d	Month 8 ± 14d	Month 12 ± 14d		
Informed Consent	X									
Demographics, medical and ocular history	Х									
Immunoassay blood sampling (ELISA and cell-based methods) ^g	х		x	x	x	x	x	x	х	
Immunoassay blood sampling (ELISPOT) ^g	Х		X	х	X	X	X	X	Х	
VFQ-25 ^h	Х							X	X	
Vital Signs	Х		X	X	X			X	X	
Weight ⁱ	X									
1										
BCVA ^k	Х		X	X	X	X	X	X	X	Х
Full ophthalmic exam ¹	X	X	X	x	X	X	X	X	X	х
SD-OCT	X		X	X	X	X	X	X	X	Х
Autofluorescence	Х			X	X	X	X	X	X	Х
Microperimetry	Х				X	X	X	X	х	
Contrast sensitivity ^m	Х					X	X	X	Х	
Colour vision	Х					X	Х	X	X	
7-field colour fundus photos ⁿ	Х							X	X	
Reading speed test ^o	X							X	X	
Randomisation	X									
Corticosteroid dispensation/accountability ^p	X	X	Х	Х	Х					

CONFIDENTIAL

Page 38 of 46

Biogen /	NightstarRx,	Ltd
BIIB111		

Visit	Visit 1ª	Visit 2 ^b	Visit 3 ^b	Visit 4 ^b	Visit 5ª	Visit 6ª	Visit 7ª	Visit 8 ^{a, c}	Early Termination ^d	Unscheduled Visit ^e
Study Day/Visit Window	Screening/ Baseline ^f	Day 0 Injection Day	Day 1 Post op	Day 7 Post op ± 3d	Month 1 ± 7d	Month 4 ± 7d	Month 8 ± 14d	Month 12 ± 14d		
Study drug/sub-retinal injection/vitrectomy/ retinal detachment		Xr								
AE/SAE monitoring ^q	Х	Х	X	X	X	Х	X	X	X	х
Concomitant medication, procedures and treatment review	х	х	х	х	х	х	х	х	х	х

Abbreviations: AE=adverse event; BCVA=best corrected visual acuity; ELISA=enzyme-linked immunosorbent assay: ELISPOT=enzyme-linked immunospot; ET=early termination; IOP=intraocular pressure; SAE=serious adverse event; SD-OCT=spectral domain optical coherence tomography; VFQ-25=25-item Visual Function Ouestionnaire.

NOTE: An attempt should be made to perform all procedures in both eyes, unless otherwise specified. Each eye should be tested separately. If the subject is unable to complete a procedure due to poor vision in either eye, this should be documented in the source notes and the assessment not completed for that eye.

Assessments with gray shading are to be assessor-masked.

- ^a Visit may be performed over 2 consecutive days if necessary.
- ^b Study Visits 2, 3, and 4 only apply to subjects in the AAV2-REP1 groups. For subjects in the Control group, a telephone contact will be made at Visits 2, 3, and 4, and information regarding AEs/SAEs and concomitant medications, procedures, and treatments will be recorded.
- c End of Study Visit.
- ^d An ET visit should be performed if a subject discontinues at any time.
- e If clinically indicated, subjects may need to return to the site for an unscheduled visit. At a minimum, all assessments listed will be performed.
- ^f Informed consent must be signed within 12 weeks prior of dosing (Visit 2). The Screening/Baseline Visit must be performed within 8 weeks of dosing (Visit 2). Assessments and procedures conducted in the final visit of the NIGHT study (including the ET Visit) may be used for the Screening/Baseline Visit if the final NIGHT study occurs within 8 weeks prior to dosing (Visit 2).
- ^g Samples will be taken and retained for analyses, if necessary.
- ^h VFQ-25: to be completed only at sites where a validated translation is available. VFQ-25 must be completed by subjects at the beginning of the study visit, before any significant interaction with the study staff.
- ⁱ Weight is assessed for dose calculation for 21-day corticosteroid regimen.

Ι....

^k In order to capture accurate BCVA values at Visit 1 (Screening/Baseline), the following conditions apply to the BCVA assessment:

CONFIDENTIAL

DocuSign Envelope ID: 9EEC395C-0D7A-4605-B5D7-D5DF30B311BC

Biogen / NightstarRx, Ltd	Statistical Analysis Plan: 273CH301 / NSR-REP-01
BIIB111	11FEB2021

If the BCVA value at Visit 1 (Screening/Baseline) is $\geq \pm 10$ letter gain or loss in the study eye compared to the previous NIGHT study visit (if applicable), then BCVA must be repeated an additional 2 times, resulting in a total of 3 BCVA measures at Visit 1. To facilitate the additional BCVA measures this visit should be conducted over 2 days, with BCVA measured twice on Day 1 and once on Day 2. All 3 BCVA values must be recorded in the eCRF. The highest score will be used to define subject eligibility.

If the BCVA value at Visit 1 (Screening/Baseline) is $\leq \pm$ 10-letter difference in the study eye compared to the previous NIGHT study visit (if applicable), then BCVA will be collected once and will not be repeated.

If the subject was not previously in the NIGHT study, BCVA assessments at baseline must be performed in triplicate over a period of 2 days, as described above. At least 2 of the triplicate values must meet BCVA eligibility requirements for inclusion in the study and the difference between the 3 assessments may not be \geq 10 letters.

- ¹ The full ophthalmic examination will include assessments of IOP and lens opacity, a slit lamp examination, and dilated ophthalmoscopy. The same slit lamp machine and lighting conditions should be used across the study for each subject.
- ^m Pelli Robson chart will be used for contrast sensitivity.
- ⁿ Stereo photos for Fields 1, 2, 3.
- ^o International Reading Speed Texts. To be completed only in languages for which a validated translation is available.
- ^p For AAV2-REP1-treated subjects, only: corticosteroid (prednisone/prednisolone) will be dispensed at Visit 1 or at least 2 days prior to Visit 2 with instruction to start treatment 2 days before the planned surgical date, and to continue for 21 days in total.
- ^q AEs/SAEs will be collected from the time the subject provides written informed consent through the End of Study Visit (or ET Visit or Unscheduled Visits, if applicable).
- ^r For subjects in the AAV2-REP1 groups only. On the Injection Day Visit (Visit 2, Day 0), all subjects in the AAV2-REP1 groups will undergo vitrectomy and treatment with AAV2-REP1.

14.3 Appendix 3: Imputation of Partial Dates

These imputation rules are limited to AE and CM partial dates only.

Partial start dates (of intervention or event)

- Case 1, day is missing (only month and year are present):
 - If year and month are same as treatment period start date then assign the day of treatment period start date to the partial date.
 - However, if end date of event or intervention is clearly before treatment period start date, assign day '01' to partial start date.
 - Otherwise, assign day of '01' to partial start date.
- Case 2, only year is present:
 - If year is same as treatment period start date then assign the month and day of the treatment period start date to the partial date.
 - However, if end date of event or intervention is clearly before treatment period start date, assign 'Jan. 01' to partial start date.
 - Otherwise, assign the month and day of 'Jan. 01' to partial start date.
- Case 3, completely missing date, no imputation is performed.

Partial end dates (of intervention or event)

- Case 1, day is missing (only month and year are present):
 - If year and month are same as study end date then assign the day of the study end date to the partial date.
 - Otherwise, assign day of last day of the month (28, 29, 30 or 31) to the partial end date.
- Case 2, only year is present:
 - If year is same as study end date then assign the month and day of the study end date to the partial date.
 - Otherwise, assign 'Dec. 31' to the partial end date.
- Case 3, completely missing date, no imputation is performed.

Note: If any partial dates have missing month, with day present, then day is ignored and also considered missing. Similarly, if year is missing, with day or month present, we handle as if the entire date is missing.

Note: If the study is ongoing and study end date is not available then the cut-off date will be used in the place of study end date. If both a cut-off date and study end date are present for a patient then the minimum of the two dates will be used as the study (or reference) end date.

14.4 Appendix 4. Multiple Imputation based on MAR – Sample SAS Code

```
*** make the data monotone missing ***;
PROC MI DATA=dset OUT=dset1 NIMPUTE=100 SEED=1234;
BY TRT:
VAR BASELINE VISIT2 VISIT3 VISIT4 VISIT5 VISIT6;
MCMC chain=multiple impute=monotone;
RUN;
*** impute to impute missing data ***;
PROC MI data=dset1 seed=1234 nimpute=1 out=dsetall;
CLASS TRT;
VAR TRT BASELINE VISIT2 VISIT3 VISIT4 VISIT5 VISIT6;
Monotone reg(VISIT2=TRT BASELINE /details);
Monotone reg(VISIT3=TRT BASELINE VISIT2/details);
Monotone reg(VISIT4=TRT BASELINE VISIT2 VISIT3 /details);
Monotone reg(VISIT5=TRT BASELINE VISIT2 VISIT3 VISIT4/details);
Monotone reg(VISIT6=TRT BASELINE VISIT2 VISIT3 VISIT4 VISIT5/details);
RUN:
```

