The rationale for including alternative data ascertainment, especially out of window visits in the primary analysis is the following: 1) It is in line with FDA and EMA guidance (U. S. Food and Drug Administration 2020, EMA 2020) on handling analysis during COVID-19 pandemic; 2) No further improvement in the treated patients is expected after the initial response around roughly 1-3 months, if any, post one-time injection of this gene therapy. Therefore, including the out of window visit, especially the visits beyond Month 12 scheduled window for the treated patients is considered a conservative approach considering potential trend of natural disease progression in the long-term follow up; 3) Very slow progression is expected in untreated control patients. The natural history study NIGHT showed an average of 0.5 letters of vision loss in untreated patients during 20 months follow up. Therefore, minimum impact on the analysis is expected from the usage of visits a few months post protocol defined window for the untreated patients, especially for the primary endpoint proportions of >= 15 letters increase from the baseline in BCVA.

Sensitivity analysis will be performed on the primary endpoint and the key secondary endpoints if applicable. The main analyses described in Section 10.1 and Section 10.2 will be repeated as follows:

- On the ITT population excluding subjects who withdraw from the study or died due to COVID-19 without any imputations, but include data collected by alternative ascertainment approaches.
- On the ITT population, where assessments performed at local non-study sites are replaced by the ad-hoc visit assessment (where available), irrespective of the interval between the ad-hoc visit and the local non-study site visit.
- On the ITT population, multiple imputation based on missing at random (MAR) will be applied to impute the data collected by alternative ascertainment approaches with Month 12 visit more than 2 months prior or 3 months after the protocol defined visit window or data missing from early termination or death due to COVID-19. In this

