analysis, with extra scientific rigor, multiple imputation will also be applied to Month 12 BCVA collected more than 2 months prior or 3 months after the visit window not due to COVID-19. Assuming the BCVA at different visits follows a multivariate normal distribution, the Monte Carlo Markov Chain (MCMC) will be implemented to impute all missing data and the Month 12 BCVA collected more than 2 months prior or 3 months after the visit window (Schafer 1997, Schafer 1999). Each imputed data for continuous endpoint, analysis of covariance (ANCOVA) model including surgical group, baseline value of the assessment, and study arms will be applied. For binary endpoint, the proportion difference and the corresponding standard error between the treatment groups (i.e. high dose vs. placebo, low dose vs. placebo) will be calculated for each imputed dataset using the two-sample Binomial test. Analysis will be performed for each of the 100 imputed datasets and results will be combined by Rubin's rule (Rubin 1976, Rubin 1987) for inference assuming the statistics estimated from each imputed dataset are normally distributed. The Sample SAS code is in Appendix 4.

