14.6 Appendix 6: Mixed Model Repeated Measures – Sample SAS Code

14.7 Appendix 7: Multiple Imputation based on MNAR – Sample SAS Code

```
*** make the data monotone missing ***;
PROC MI DATA=dset OUT=dset1 NIMPUTE=100 SEED=1234;
BY TRT:
VAR BASELINE VISIT2 VISIT3 VISIT4 VISIT5 VISIT6;
MCMC chain=multiple impute=monotone;
RUN;
*** for control arm, use all available data to impute missing data ***;
PROC MI DATA=dset1(where=(TRT='Placebo')) out=dset2 nimpute=1 seed=1235;
BY IMPUTATION ;
VAR BASELINE VISIT2 VISIT3 VISIT4 VISIT5 VISIT6;
MONOTONE REG(VISIT2=BASELINE/details);
MONOTONE REG(VISIT3=BASELINE VISIT2/details);
MONOTONE REG(VISIT4=BASELINE VISIT2 VISIT3/details);
MONOTONE REG(VISIT5=BASELINE VISIT2 VISIT3 VISIT4/details);
MONOTONE REG(VISIT6=BASELINE VISIT2 VISIT3 VISIT4 VISIT5/details);
RUN;
*** for active arm, impute missing data on VISIT2 using control arm ***;
PROC MI DATA=dset1(where=((TRT='Active' and VISIT2=.) or (TRT='Placebo'
                                                                                 and
VISIT2>.))) out=dset3 nimpute=1 seed=1235;
BY IMPUTATION ;
VAR BASELINE VISIT2;
MONOTONE REG(VISIT2=BASELINE/details);
RUN;
*** for active arm, impute missing data on VISIT3 using control arm ***;
PROC MI DATA=dset3(where=((TRT='Active' and VISIT3=.) or (TRT='Placebo'
                                                                                 and
VISIT3>.))) out=dset4 nimpute=1 seed=1235;
BY IMPUTATION ;
VAR BASELINE VISIT2 VISIT3;
MONOTONE REG(VISIT3=BASELINE VISIT2/details);
RUN:
*** repeat the same method for each sequential visit in active arm ***;
*** set all data together ***;
*** DSETX is the subset of active subjects with missing on VISIT2 ***;
*** DSETY is the subset of active subjects without missing on VISIT2 ***;
Data dsetall;
Set dset2 dsetX dsetY;
RUN:
*** Analyze the data on the last timepoint by ANCOVA ***;
PROC MIXED data=dsetall;
BY IMPUTATION ;
CLASS TRT;
MODEL CHG=BASELINE TRT;
LSMEANS TRT / PDIFF CL;
ESTIMATE "High vs Control" TRT 1 0 -1;
ESTIMATE "Low vs Control" TRT 0 1 -1;
ODS OUTPUT LSMEANS=LSMEAN;
ODS OUTPUT ESTIMATES=LSEST;
RUN:
*** Use Rubin's Rule ***;
PROC MIANALYZE parms=lsest;
BY LABEL;
MODELEFFECTS ALLEST;
ODS OUTPUT PARAMETERESTIMATES=PARMS;
RUN:
```

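### The second imputation step in SAP Appendix 4 has no BY on the imputation number, so the missing-at-random sensitivity analysis reports standard errors that are too small

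*SAP*

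**What the plan says.** SAP 5.5 (COVID-19 handling) specifies a sensitivity analysis of the primary and key secondary endpoints: "On the ITT population, multiple imputation based on missing at random (MAR) will be applied to impute the data collected by alternative ascertainment approaches" when Month 12 was measured far outside its window, and to impute values lost through COVID-19 withdrawal or death. It extends this to far out-of-window Month 12 readings that have nothing to do with COVID-19. On pooling it says: "Analysis will be performed for each of the 100 imputed datasets and results will be combined by Rubin's rule". It sends the reader to Appendix 4 for the code.

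Appendix 4 has two imputation steps:

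- **Step 1** is "PROC MI DATA=dset OUT=dset1 NIMPUTE=100 SEED=1234", run by treatment arm, with "MCMC chain=multiple impute=monotone". It makes 100 copies and fills only enough gaps to leave a monotone pattern. A value missing at the end of a subject's series stays missing in every copy.
- **Step 2** is "PROC MI data=dset1 seed=1234 nimpute=1 out=dsetall". CLASS, VAR and the regression statements follow, ending with "Monotone reg(VISIT6=TRT BASELINE VISIT2 VISIT3 VISIT4 VISIT5/details" for the last visit. There is no BY statement.

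Appendix 7 (control-based imputation) also follows a 100-copy first step with a single-imputation regression step: "PROC MI DATA=dset1(where=(TRT='Placebo')) out=dset2 nimpute=1 seed=1235". There, each second-stage call shown carries "BY IMPUTATION" (the SAS variable is `_IMPUTATION_`). The ANCOVA in Appendix 4 (14.4.1) is run by imputation as well.

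**The concern.** Step 2 is the step that fills the trailing Month 12 values. Without a BY statement it treats the 100 copies of each subject as 100 independent subjects. The regression coefficients and residual variance are drawn once, with a precision the trial does not have, and that draw serves all copies.

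Rubin's rules rely on the spread of estimates across imputations to carry two things: residual noise in the imputed values and uncertainty about the imputation model. Here the second part all but disappears, so intervals come out too narrow. This is the wrong direction for an analysis whose purpose is to challenge the main results.

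**Working it through.** **The plan's own figures.** The SAP gives no standard error and no expected missing rate for this analysis, so there is no figure of its own to reproduce. Its only design calculation, the Fisher power in SAP 3.6, is not an input here.

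**Mechanism.** For one visit's regression on n subjects with k coefficients, a proper imputation draws

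- σ*² = RSS / χ²(n − k)
- β* ~ N(β̂, σ*² (X′X)⁻¹)

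separately for each of the M = 100 copies. Stacking the copies replaces RSS by 100·RSS, X′X by 100·X′X and the degrees of freedom by 100n − k. The variance of β* is divided by 100 (its SD by 10), and there is one draw instead of 100. The pooled variance is T = W̄ + (1 + 1/M)·B, where W̄ is the mean within-imputation variance and B the between-imputation variance. With BY, B contains residual and parameter components. As written, B contains essentially the residual component alone.

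**Inputs from the SAP.** Arms of 64, 32 and 64 (3.6); 100 imputations; last-visit regression on arm, baseline and earlier visits (Appendix 4); ANCOVA on arm and baseline (14.4.1).

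**Assumptions not in the SAP.** SD of 10 letters; equal correlation of 0.5 or 0.8 between visits; high-dose effect of 3 letters; 5% to 40% of Month 12 values missing at random; all other data complete; each copy keeps its imputation number. There were 400 simulated trials per scenario.

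**Results for high dose versus control, change from baseline.** The last column is the standard-error ratio (as written / with BY) for the difference in the proportion gaining 15 letters or more.

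| Correlation | Missing | SE with BY | SE as written | Ratio | Ratio of B | Binary SE ratio |
|---|---|---|---|---|---|---|
| 0.5 | 5% | 1.568 | 1.558 | 0.994 | 0.812 | 0.997 |
| 0.5 | 10% | 1.611 | 1.591 | 0.987 | 0.801 | 0.992 |
| 0.5 | 20% | 1.692 | 1.632 | 0.965 | 0.699 | 0.981 |
| 0.5 | 30% | 1.804 | 1.680 | 0.931 | 0.590 | 0.966 |
| 0.5 | 40% | 1.934 | 1.713 | 0.886 | 0.494 | 0.943 |
| 0.8 | 5% | 1.094 | 1.089 | 0.995 | 0.849 | 0.989 |
| 0.8 | 10% | 1.109 | 1.097 | 0.989 | 0.801 | 0.982 |
| 0.8 | 20% | 1.157 | 1.121 | 0.969 | 0.698 | 0.960 |
| 0.8 | 30% | 1.226 | 1.154 | 0.941 | 0.605 | 0.939 |
| 0.8 | 40% | 1.310 | 1.178 | 0.899 | 0.498 | 0.908 |

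For scale, at correlation 0.5 the 95% half-width falls from 1.96 × 1.692 = 3.32 to 1.96 × 1.632 = 3.20 letters with 20% missing. With 40% missing it falls from 1.96 × 1.934 = 3.79 to 1.96 × 1.713 = 3.36 letters.

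**Which standard error is right.** At correlation 0.5 and 40% missing, the estimates varied across simulated trials with an SD of 1.941 with BY and 1.935 as written. The BY standard error (1.934) matches this; the as-written one (1.713) does not. At correlation 0.8 the SDs are 1.312 and 1.301, against standard errors of 1.310 and 1.178. Coverage at 40% missing was 95.5% and 94.5% with BY, and 93.5% and 91.5% as written. The Monte Carlo error of a coverage figure is √(0.95 × 0.05 / 400) ≈ 1.1 points, so coverage cannot resolve the smaller effects.

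**If the imputation number is lost.** Should the second PROC MI reset the index to 1, the ANCOVA would treat all 100 copies as one trial. Its standard error would be smaller by about √100 = 10, and Rubin's rule would have nothing to combine. The documents cannot settle whether this happens, and the table does not depend on it.

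**The case against.** The strongest reply is that the code is labelled as a sample and the governing text is right: SAP 5.5 requires 100 separate analyses pooled by Rubin's rule. The sample cannot be the final program in any case. Its ANCOVA omits surgical group, which 5.5 requires, and Appendix 7 uses a two-level active/placebo label for a three-arm trial. The consequence is also narrow. This is one of several COVID-19 sensitivity analyses; the primary test (SAP 10.1) and the main key secondary analyses (10.2) do not use it; and 10.4 has further missing-data analyses. At 10% missing or less the continuous-endpoint shortfall is about 1% or less. Finally, a line could have been lost when the PDF was read.

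The limits on consequence and size stand. The sample-code defence does not. SAP 5.5 points to Appendix 4 for implementation and nowhere else says how the second step handles the 100 copies. Its prose has MCMC imputing everything, which is not what the code does, so it cannot fill the gap. A lost line is unlikely: the BY line in step 1 of the same code survived, as did those in 14.4.1 and Appendix 7. The two appendices do differ in model (Appendix 4 pools arms with treatment as a term, Appendix 7 fits control data), but that gives no reason to drop the BY in one of them.

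**Conclusion.** The concern holds. As written, the missing-at-random analysis understates its standard errors, and Appendix 4 conflicts with Appendix 7 and with SAP 5.5. For the continuous endpoint the shortfall is about 0.5% at 5% imputed, 1% at 10%, 3-4% at 20%, 6-7% at 30% and 10-11% at 40%. For the binary endpoint it is about 2-4% at 20% and 6-9% at 40%. Between-imputation variance falls by about 20% at 10% imputed and by half at 40%.

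These sizes rest on the assumed SD, correlations and missing fractions, and on each copy keeping its imputation number. The direction follows from the mechanism and was the same in every scenario. The imputed share may exceed ordinary dropout, because far out-of-window Month 12 readings are replaced too. Point estimates are essentially unaffected, and the primary conclusion does not depend on this step. It should be corrected because the error bars are wrong as specified.

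**What to change.** In Appendix 4, sort `dset1` by imputation number and add `BY _IMPUTATION_;` to the second PROC MI, as Appendix 7 does. The sort is needed because step 1 runs by arm, so its output may not be in imputation order. Then confirm that `dsetall` still holds imputation numbers 1 to 100 before the ANCOVA and the binary analysis. The cost is a sort and one line of code, with slightly wider intervals. Design, conduct and the primary analysis do not change.
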